8. STATISTICAL METHODOLOGY

8.1. General

Listings will be provided for all data captured in the database. Listings will include all subjects assigned to the all subjects population and include data up to the point of study completion or discontinuation. Subjects are generally considered to have completed the study if they completed all protocol-specified procedures and assessments for the EOS visit. Any subject who discontinued the study will be identified accordingly in the listings. Summaries and statistical analyses will include the subjects assigned to the relevant population based on data type.

Data analysis will be performed using the SAS® statistical software package Version 9.4 (or higher if upversioned during the study).

Analysis Data Model (ADaM) datasets will be prepared using Clinical Data Interchange Standards Consortium (CDISC) ADaM Version 2.1 (or higher if upversioned during the study) and CDISC ADaM Implementation Guide Version 1.2 (or higher if upversioned during the study). Pinnacle 21 Community Validator Version 3.1.0 (or higher if upversioned during the study) will be utilized to ensure compliance with CDISC standards.

Caution should be used when interpreting results from the statistical analyses conducted in this study because the sample size is not based on power calculations.

Where reference is made to 'all calculations', this includes, but is not limited to, summary statistics, statistical analyses, baseline derivation, changes from baseline and any parameter derivations.

8.1.1. Calculation of the Summary Statistics

For continuous data the following rules will be applied:

- Missing values will not be imputed, unless specifically stated otherwise.

- Unrounded data will be used in the calculation of summary statistics.
- If the number of subjects with valid observations (n) <3, summary statistics will not be calculated, with the exception of n, minimum, and maximum.
- As ET data is not associated with any scheduled timepoint, it will be excluded from all calculations of summary statistics.
- Postdose repeats and unscheduled assessments will not be included in calculations of summary statistics.

For categorical data the following rules will be applied:

- If the categories of a parameter are ordered (eg, AE severity), all categories between the possible minimum and maximum categories will be included, even if n = 0 for a given category. If the categories are not ordered (eg, race), only those categories for which there is at least 1 subject represented will be included.
- Missing values will not be imputed, with the exception of AEs where the ‘worst-case’ approach will be taken (see [Section 8.6.1](#)), or unless specifically stated otherwise. A ‘missing’ category will be included for any parameter for which information is missing. This will ensure that the population size totals are consistent across different parameters.

All protocol deviations and data issues (eg missing data, out of protocol window) that occur during the study, including those related to COVID-19, will be considered prior to database lock for their severity/impact on how the data will be displayed.

8.1.2. Repeat and Unscheduled Readings

For vital signs measurements and ECG data only, any predose value recorded in addition to the original value or a postdose value recorded within 15 minutes of the original value will be defined as a repeat value; any postdose value recorded more than 15 minutes after the original value will be defined as an unscheduled value. For all other data types (eg, laboratory parameters), any value recorded in addition to the original value will be defined as an unscheduled value.

The original scheduled value will be used in all calculations post dose. In the event of any repeats or unscheduled measurements taken pre-dose the values will be considered when determining the baseline value.

Post dose repeats, unscheduled assessments, and ET measurements will be excluded from all calculations, with the exception of the baseline derivation (see [Section 8.1.3](#)).

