8.1.3. Definitions of Baseline and Change from Baseline

The baseline will be defined as the last non-missing measurement before administration of study drug on Day 1, Period 1.

If the date/time of the value is incomplete or missing, it will be excluded from the baseline calculation, unless the incomplete date/time indicates the value was recorded prior to dosing.

Individual changes from baseline will be calculated by subtracting the individual subject's baseline value from the value at the timepoint. The mean change from baseline will be defined as the mean of the individual changes from baseline for all subjects.

See [Section 8.1.2](#) for more detail on handling repeat and unscheduled readings in the calculations.

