8.6.2. Clinical Laboratory Parameters

All clinical laboratory parameters, with changes from baseline, will be listed; any value outside the clinical reference range will be flagged, and whether the out of range value was deemed clinically significant or not clinically significant will be indicated.

The observed results and change from baseline for clinical chemistry, hematology, and coagulation parameters will be summarized descriptively by timepoint. Values recorded as $\text{<}x$, $\leq x$, $\geq x$, or $\text{>}x$ will be displayed in the listings as recorded. For the derivation of listing flags, calculation of summary statistics, $\text{<}x$ and $\leq x$ values will be set to 0, whereas $\geq x$ and $\text{>}x$ values will be set to x.

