8.6.3. Vital Signs Parameters

All vital signs parameters, with changes from baseline, will be listed; any value outside the clinical reference range will be flagged, and whether the out of range value was deemed clinically significant or not clinically significant will be indicated.

The observed results and change from baseline for all vital signs results will be summarized descriptively by treatment and timepoint.

8.6.4. 12-lead Electrocardiogram Parameters

All 12-lead ECG parameters, with changes from baseline, will be listed; any value outside the clinical reference range will be flagged, and whether the out of range value was deemed clinically significant or not clinically significant will be indicated.

The observed results and change from baseline for all 12-lead ECG parameters will be summarized descriptively by treatment and time point. QTcF values that are > 450 msec and increase from baseline > 30 msec will be flagged in the data listing.

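### SAP 8.1.2, read with the definition in 8.1, bars postdose repeat, unscheduled and early-termination values from change from baseline, which conflicts with the listings in 8.6.2 to 8.6.4 and disables the QTcF increase criterion for those records

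*SAP*

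**What the plan says.** Four parts of the SAP bear on this.

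- **Definition (8.1).** Of the term 'all calculations', the SAP says "this includes, but is not limited to, summary statistics, statistical analyses, baseline derivation, changes from baseline and any parameter derivations".
- **Exclusion (8.1.2).** "Post dose repeats, unscheduled assessments, and ET measurements will be excluded from all calculations, with the exception of the baseline derivation". The same section says "The original scheduled value will be used in all calculations post dose". For vital signs and ECGs, an extra postdose reading is a repeat if taken within 15 minutes of the scheduled one and unscheduled if later. For other data, any extra reading is unscheduled.
- **Change from baseline (8.1.3).** "Individual changes from baseline will be calculated by subtracting the individual subject's baseline value from the value at the timepoint". The section then sends the reader back to 8.1.2 for repeat and unscheduled readings.
- **Listings and flags (8.6.2 to 8.6.4).** For laboratory data, "All clinical laboratory parameters, with changes from baseline, will be listed"; for ECGs, "All 12-lead ECG parameters, with changes from baseline, will be listed". Section 8.6.3 says the same of vital signs. All three also flag values outside the reference range and show the judgement of clinical significance. Section 8.6.4 adds: "QTcF values that are > 450 msec and increase from baseline > 30 msec will be flagged in the data listing".

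SAP 8.1.1 has its own exclusion of ET, postdose repeat and unscheduled values, but confines it to summary statistics.

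**The concern.** Keeping ET, repeat and unscheduled values out of by-timepoint means is normal practice. Keeping them out of the individual change from baseline is a different matter, because that derivation feeds the listings and the QTcF flag.

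Safety is the secondary objective and has no inferential analysis (SAP 8.6.6). The SAP specifies no worst-post-baseline or categorical QTcF summary. Since 8.1.1 already removes these values from the summary tables, the listing is the only planned place where their change could appear.

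Such records are foreseeable. Protocol Appendix 4 schedules ECGs and laboratory tests at ET. Protocol 4.6 allows withdrawal for adverse events, with efforts to complete the ET assessments. Protocol 7.3 and 7.3.1 allow repeated and additional safety tests. Protocol 1.6 names falls in white cell counts as a potential risk, and for those a change can be informative while the value is still within range.

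**Working it through.** The plan gives no figure to reproduce. The check follows the rules in order and then applies them to example values.

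**Does the exclusion reach change from baseline?**

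1. SAP 8.1 names changes from baseline as one of the calculations covered by the term.
2. SAP 8.1.2 excludes postdose repeats, unscheduled assessments and ET measurements from that term and exempts only the baseline derivation. Change from baseline stands beside baseline derivation in the 8.1 list and is not exempted.
3. SAP 8.1.3 uses the value at a timepoint and defers to 8.1.2. SAP 8.1.1 says ET data belong to no scheduled timepoint.
4. So, as written, these records have no change from baseline.

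**Does this conflict with other text?** Yes. SAP 8.6.2 to 8.6.4 promise changes for all listed parameters, and SAP 8.1 promises listings of all captured data. For an ET or unscheduled record, both instructions cannot be followed. SAP 8.1.1 draws the narrower line, and no rule says which section prevails.

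**What happens to the QTcF flag?** Let V be the value and B the baseline; the change is V − B, and is undefined for an excluded record. The sentence in 8.6.4 can be read in two ways:

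- Joint (the literal wording): flag if V > 450 and V − B > 30.
- Two separate flags: flag if V > 450; flag if V − B > 30.

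The values below are hypothetical and in msec. 'Derived' means a scheduled record, or any record after the fix. 'Excluded' means a record barred by 8.1.2.

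| B | V | V − B | Joint, derived | Joint, excluded | Two flags, derived | Two flags, excluded |
|---|---|---|---|---|---|---|
| 410 | 465 | +55 | flagged | not flagged | flagged | flagged (V > 450) |
| 400 | 445 | +45 | not flagged | not flagged | flagged | not flagged |
| 430 | 455 | +25 | not flagged | not flagged | flagged | flagged (V > 450) |

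Under the joint reading no excluded record can be flagged, because one of the two conditions can never be evaluated; the first row shows the loss. Under the two-flag reading the criterion on the value still works, and the criterion on the increase fails (second row). The increase criterion is therefore inoperative for excluded records under either reading.

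**Laboratory data.** SAP 8.6.2 has a reference-range flag only, which needs no change from baseline. What is lost there is the printed change, not a flag.

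**The case against.** The strongest reply is that this is loose drafting, not a decision. The specific listing sections say all parameters are listed with changes, 8.1.1 limits its exclusion to summary statistics, and 8.1.2 exempts baseline derivation from a rule about postdose values, where it has little meaning. SAP 8.6.2 also names the derivation of listing flags separately from summary statistics. On that view 8.1.2 governs tables and 8.6.2 to 8.6.4 govern listings. The listing layouts are in the TFL shells, which are not among the documents.

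This may well be the intent. But 8.1 defines the term expressly, and the wider wording of 8.1.2 would add little if it only repeated 8.1.1. Two programmers could reasonably produce different listings. An appeal to intent is a reason to correct the sentence.

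Other objections stand and limit the point:

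- A reader might infer that safety data are lost. They are not: the values are listed, with range and clinical-significance flags.
- A reader might infer a bias toward LOXO-305 looking clean on QTcF or white cells. The documents do not support that. If an abnormal scheduled value prompts a repeat, the scheduled value keeps its change and stays in the tables; dropping a normal repeat can even preserve an abnormality that resolved.
- A reader might infer that a signal would go unseen. Protocol 7.3.1 records adverse events noted on ECG or laboratory evaluation, Protocol Appendix 1 counts clinically significant laboratory changes as adverse events, and SAP 8.6.1 tabulates treatment-emergent events, including those leading to discontinuation.

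**Conclusion.** The point holds as an internal contradiction with a specific consequence. Taken literally, 8.1 with 8.1.2 leaves postdose repeat, unscheduled and ET records without a change from baseline, contrary to 8.6.2 to 8.6.4. It also makes the increase criterion of the QTcF flag impossible to meet for those ECGs. That the flag fails altogether rests on reading 8.6.4 as one joint condition, which is its literal wording.

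The size is small. Only listings of descriptive safety data in up to 16 subjects are affected. The records that matter most are ET values, and unscheduled values taken because of an event and worse than the scheduled ones. The documents give no expected number of either, so no rate is offered, and the QTcF examples show only how the rule works. It is still worth correcting, because the rule as written would give an incomplete safety listing and the correction costs almost nothing.

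**What to change.** In SAP 8.1.2, limit the exclusion of postdose repeats, unscheduled assessments and ET measurements to summary statistics, matching 8.1.1. Add that individual change from baseline and the QTcF listing flag are derived for every postdose record, including repeat, unscheduled and ET records. It would help to say in 8.6.4 whether the QTcF flag is one joint condition or two. A worst-post-baseline line per subject is optional and not needed to resolve the conflict.

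The cost is a sentence or two of SAP text and a minor change to listing programs before database lock. No new data are needed.

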8.1.3. Definitions of Baseline and Change from Baseline

The baseline will be defined as the last non-missing measurement before administration of study drug on Day 1, Period 1.

If the date/time of the value is incomplete or missing, it will be excluded from the baseline calculation, unless the incomplete date/time indicates the value was recorded prior to dosing.

Individual changes from baseline will be calculated by subtracting the individual subject's baseline value from the value at the timepoint. The mean change from baseline will be defined as the mean of the individual changes from baseline for all subjects.

See [Section 8.1.2](#) for more detail on handling repeat and unscheduled readings in the calculations.

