8.4. Safety Analysis

All safety assessments, including AEs, SAEs, vital sign measurements, clinical laboratory results, physical examination results, concomitant medications, and 12-lead ECGs, will be tabulated and summarized where possible, using descriptive methodology, as needed, by timepoint. Unless otherwise specified, baseline value is defined as the last non-missing measurement before administration of study drug on Day 1, Period 1. No formal statistical analyses are planned for the safety data. All safety data will be listed by subject.

Concomitant medications will be coded using the World Health Organization (WHO) Drug Dictionary (WHO Drug Global B3, September 2019). Adverse events will be coded using Medical Dictionary for Regulatory Activities (MedDRA) Version 22.1 (or higher). The incidence of AEs will be presented by severity and by relationship to study drug as determined by the Investigator or designee ([Appendix 1](#) for AE reporting). All TEAEs will be summarized by system organ class and preferred term.

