- o. Clinical chemistry panel (fasted for at least 8 hours), coagulation parameters, hematology panel, and UA will be performed at Screening, Check-in (Day -1), Day 2 (24 hours postdose on Day 1), Day 6 (predose), Day 12 (predose), Day 15 (predose), Day 17 (predose), Day 20 (24 hours postdose on Day 19), and Day 22 (72 hours postdose on Day 19, if the subject completes the study [EOT]), or on the day of ET. At ET or the day before EOT (Day 22), subjects are not required to be fasted prior to clinical laboratory evaluations.
- p. Testing for COVID-19 will be conducted at a minimum at Screening and Check-in (Day -1). Testing for COVID-19 may also be conducted periodically during the subject's CRU confinement, at the discretion of the Investigator (or designee). Tests will be performed by rapid polymerase chain reaction or equivalent.
- q. Urine drug screen for drugs of abuse (including cotinine) and alcohol screen (urine or breath).
- r. Prior and concomitant medication administration will be recorded beginning at informed consent. In addition, all Investigator-approved prescription and over-the-counter medications taken by a subject within 14 days or 5 half-lives (if known), whichever is longer, prior to Day 1 will be recorded on the subject's electronic CRF.
- s. Female subjects only. Performed at Screening, Check-in (Day -1), and Day 22 (72 hours postdose on Day 19), if the subject completes the study (EOT) or on the day of ET.
- t. Post-menopausal female subjects only.
- u. End of Treatment is defined as when the subject is released from the CRU following completion of all assessments through Day 23. Early Termination is defined as when the subject is released from the CRU if the subject terminates the study early. Vital sign measurements, ECG, and abbreviated physical examination results are to be available for review by the Investigator (or designee) prior to subject release from the CRU on Day 23 (EOT) or ET. Clinical laboratory results (for clinical chemistry, hematology, coagulation, and UA) and serum pregnancy test results (female subjects only) are to be available for review by the Investigator (or designee) prior to subject release from the CRU at the EOT visit and prior to subject release from the CRU at the ET visit if available.

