2.2. Secondary Objective

The secondary objective of the study is to assess the safety and tolerability of multiple oral doses of LOXO-305 when administered alone, and coadministered with a single oral dose of probe drug cocktail.

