4. STUDY DESIGN

This is a Phase 1, open-label, 2-period, fixed-sequence drug-drug interaction study to investigate the effect of multiple oral doses of LOXO-305 on the PK of single oral doses of caffeine (CYP1A2 substrate) and its metabolite paraxanthine, S-warfarin (CYP2C9 substrate), and omeprazole (CYP2C19 substrate) in healthy subjects.

In Period 1, Day 1, 200 mg caffeine (tablet), 40 mg omeprazole (capsule), and 10 mg warfarin (tablet) administered as a single dose of probe drug cocktail, along with 10 mg vitamin K (tablets), will be administered in the morning following a fast of at least 10 hours predose and 2 hours postdose. Blood samples for concentrations of the substrates (caffeine/paraxanthine, omeprazole, and S-warfarin) in plasma will be collected predose through 120 hours postdose on Day 1. Of these samples, samples will be analyzed for concentrations of caffeine/paraxanthine from predose through 24 hours postdose, for concentrations of omeprazole [REDACTED], and for concentrations of [REDACTED].

There will be a washout period of 5 days between administration of the probe drug cocktail on Day 1 and the first dose of LOXO-305 on Day 6.

[figure not shown]
In Period 2, on Days 6 through 19, oral doses of 200 mg LOXO-305 will be administered once daily (QD) for 14 consecutive days in the morning at the actual time of the Day 1 probe drug cocktail dosing (\pm 1 hour). On Day 15, LOXO-305 will be coadministered with 200 mg caffeine (tablet), 40 mg omeprazole (capsule), and 10 mg warfarin (tablet) administered as a single dose of probe drug cocktail, along with 10 mg of vitamin K (tablets) at the actual time of the Day 1 probe drug cocktail dosing (\pm 1 hour) following a fast of at least 10 hours predose and 2 hours postdose. On Days 7 through 11, and Days 13, 14, 16, 18, and 19, subjects will fast for at least 2 hours predose and 1-hour postdose. On Days 6, 12, and 17 where clinical laboratory evaluations are performed, subjects will fast for at least 8 hours predose and 1 hour postdose. Blood samples for concentrations of LOXO-305 in plasma will

CCI

CCI. Samples collected CCI. CCI LOXO-305 dosing CCI. Blood samples for concentrations of the substrates (caffeine/paraxanthine, omeprazole, and S-warfarin) in plasma will be CCI; of these samples, samples will be analyzed for concentrations of caffeine/paraxanthine from CCI, for concentrations of omeprazole CCI, and for concentrations of CCI.

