8.6. Safety and Tolerability Assessments

8.6.1. Adverse Events

All AEs will be coded using the Medical Dictionary for Regulatory Activities (MedDRA) Version 23.0. All AEs will be assigned severity grade using National Cancer Common Terminology Criteria for Adverse Events (CTCAE) Version 5.0.

A treatment-emergent adverse event (TEAE) will be defined as an AE that starts during or after the first dose, or starts prior to the first dose and increases in severity after the first dose.

A treatment-related TEAE will be defined as a TEAE with a relationship of related to the study treatment LOXO-305 and probe drugs and vitamin K, as determined by the investigator.

The assignment of TEAEs to the treatments will be as follows:

- A TEAE occurring during or after Day 1 dosing and prior to Day 6 dosing will be assigned to Probe Drug Cocktail/or 10 mg vitamin K
- A TEAE occurring during or after Day 6 dosing and prior to Day 15 dosing will be assigned to 200 mg LOXO-305
- A TEAE occurring during or after Day 15 dosing will be assigned to 200 mg LOXO-305 + Probe Drug Cocktail/or 10 mg vitamin K

All AEs will be listed. In addition to the data recorded in the database, the listings will include derived onset time and duration. Onset time will be calculated from the time of the last dose for TEAEs only.

The frequency of subjects with TEAEs and the number of TEAEs will be summarized for the following categories:

- TEAEs (overall, serious, leading to discontinuation, and leading to death) by treatment
- TEAEs by severity and treatment
- Treatment-related TEAEs (overall, serious, leading to discontinuation, and leading to death) by treatment
- Treatment-related TEAEs by severity and treatment

The frequency of subjects will be summarized separately for TEAEs and treatment-related TEAEs by the following:

- System organ class, preferred term, and treatment
- Preferred term and treatment

For the AE data the following rules will apply:

- For the derivation of TEAE status: If the start date/time of an AE is incomplete or missing, an AE will be assumed to be a TEAE, unless the incomplete start date/time or the end date/time indicates an AE started prior to the first dose.
- For the derivation of treatment-related TEAE status: If the study treatment relationship for a TEAE is missing, a TEAE will be assumed to be a treatment-related TEAE.

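### With one pre-cocktail safety baseline, changes reported for LOXO-305 alone include any shift that arose before its first dose; a Day 6 baseline can be added from data already scheduled

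*SAP*

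**What the plan says.** SAP 8.1.3 defines one baseline: "The baseline will be defined as the last non-missing measurement before administration of study drug on Day 1, Period 1". It then applies it everywhere: "Individual changes from baseline will be calculated by subtracting the individual subject's baseline value from the value at the timepoint". Protocol 8.4 gives the same definition but leaves room for an exception: "Unless otherwise specified, baseline value is defined as the last non-missing measurement before administration of study drug on Day 1, Period 1". The SAP specifies none for Period 2.

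The secondary objective (SAP 2.2) covers the "safety and tolerability of multiple oral doses of LOXO-305 when administered alone, and coadministered with a single oral dose of probe drug cocktail". Adverse events already follow that split, because SAP 8.6.1 states: "A TEAE occurring during or after Day 6 dosing and prior to Day 15 dosing will be assigned to 200 mg LOXO-305".

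SAP 8.6.3 and 8.6.4 summarize vital sign and ECG changes by treatment and timepoint, and SAP Table 3 gives 200 mg LOXO-305 QD its own safety label. SAP 8.6.2 summarizes chemistry, hematology and coagulation by timepoint only. The QTcF flag in SAP 8.6.4 refers to values above 450 msec and to increases from baseline above 30 msec.

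**The concern.** LOXO-305 is first given five days after the cocktail and vitamin K, and after five days of confinement and serial blood sampling. A change measured from before Day 1 therefore covers more than LOXO-305, even where the table labels it as LOXO-305 treatment. A Period 1 shift in the same direction as a LOXO-305 effect would inflate the reported change, and an opposite shift would offset it. White cell counts are of particular interest, because Protocol 1.6 names their decrease as a potential risk of multiple dosing. Adverse events restart their attribution at Day 6, but the continuous safety measures are not re-referenced there.

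**Working it through.** The plan states no figure to reproduce. The check compares the baseline rule with the assessment schedule, then looks at the algebra.

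**1. What is measured, and when (Protocol Appendix 4, footnotes e to h and o)**

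| Parameter | Baseline under SAP 8.1.3 | Day 6 predose value | Values in the LOXO-305-alone window |
|---|---|---|---|
| 12-lead ECG; supine BP and pulse | Day 1 predose | Yes | Day 6 at 2 h, Day 12 predose, Day 15 predose |
| Chemistry, hematology, coagulation | Normally Check-in (Day -1); no Day 1 predose sample | Yes | Day 12 predose, Day 15 predose |
| Temperature, respiratory rate | Normally Check-in (Day -1) | No | None |
| Oxygen saturation | Day 1 predose | No | None |

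Every parameter measured in the LOXO-305-alone window also has a scheduled Day 6 predose value. The three without one are not measured in that window.

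**2. What the reported change contains**

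For any time t after Day 6 dosing:

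V(t) - V(baseline) = [V(t) - V(Day 6 predose)] + [V(Day 6 predose) - V(baseline)]

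The second bracket, d, is complete before any LOXO-305 is given. With the planned baseline it enters the reported change in full. With a Day 6 baseline its contribution is 0.

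**3. Illustration for the increase part of the QTcF flag**

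The documents give the 30 msec threshold (SAP 8.6.4) and up to 16 subjects (Protocol 8.1). The rest is assumed: no LOXO-305 effect, one independent, normally distributed reading per subject, SD of QTcF change 8 to 12 msec from either baseline, and Period 1 shift d of 0, 5 or 10 msec.

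p = 1 - Φ((30 - d)/SD); P(at least one of 16) = 1 - (1 - p)^16

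For SD 10, the standardized distances are 30/10 = 3.0, 25/10 = 2.5 and 20/10 = 2.0, so p = 0.0013, 0.0062 and 0.0228.

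| SD (msec) | d = 0 | d = 5 | d = 10 |
|---|---|---|---|
| 8 | 0.1% | 1.4% | 9.5% |
| 10 | 2.1% | 9.5% | 30.8% |
| 12 | 9.5% | 26.0% | 54.3% |

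With a Day 6 baseline the d = 0 column applies whatever d was. In the other direction, a Period 1 fall of 15 msec means that a true rise must exceed 30 + 15 = 45 msec to pass the criterion, so true rises between 30 and 45 msec would be missed. Neither calculation covers the 450 msec part of the flag.

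**The case against.** The best defence is that this is a consistent and legitimate choice. The protocol and SAP agree on one untreated reference, which shows cumulative change since before any study drug. SAP 8.6.6 plans no inferential safety analysis, so no test or decision depends on it. Day 6 predose is a scheduled timepoint, so a Period 1 shift would appear in the tables before the later LOXO-305 rows. All of this stands and lowers the weight of the point.

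Several stronger readings are tempting, but the documents do not support them:

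- **That the LOXO-305 changes are in fact distorted.** No Period 1 shift is shown. If the 36 cocktail samples in Protocol Appendix 3 split equally by period, 18 × 4 = 72 mL plus 4 + 4 + 3 = 11 mL of Day 2 laboratory samples gives about 83 mL drawn before the Day 6 value. That volume does not translate into a change in any parameter, white cells included. If S-warfarin had a half-life of 20 to 40 h (assumed), 2^(-120/20) = 1.6% to 2^(-120/40) = 12.5% would remain at 120 h. That is a plasma fraction, not a coagulation effect, and Protocol 3.2 gives vitamin K to counteract warfarin.
- **That changes from Day 6 cannot be recovered for a subject.** Protocol 8.4 and SAP 8.6.2 to 8.6.4 list the values and changes, so one listed change can be subtracted from another by hand.
- **That hematology and coagulation are tabulated as LOXO-305 alone.** Those tables carry no treatment label; only their Day 12 and Day 15 predose rows carry the shift.
- **That all vital signs have a Day 6 value.** Temperature, respiratory rate and oxygen saturation do not.

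A Day 6 baseline also does not isolate LOXO-305. Confinement and blood sampling continue, and there is no concurrent control.

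**Conclusion.** The point holds as a modest, inexpensive improvement. It is not an error in the plan, nor a contradiction between the documents. The planned changes after Day 6 dosing carry any Period 1 shift one for one, and the secondary objective asks about LOXO-305 given alone.

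A reader can subtract mean changes across rows if the same subjects contribute, and individual changes from the listings. The planned summaries still give no SD of change from Day 6, and the QTcF increase is never flagged against Day 6. How much this matters depends on the size of d, which the documents do not give. The QTcF percentages show sensitivity under assumed values and do not predict what this study will find.

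**What to change.** In SAP 8.1.3, add a Period 2 baseline for 12-lead ECG, supine blood pressure, pulse and laboratory parameters only. Define it as the latest available value recorded after Day 1 dosing and before the first LOXO-305 dose on Day 6. The lower limit stops a missing Day 6 value from falling back to a pre-cocktail one.

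Present change from this baseline for timepoints after Day 6 dosing, and apply the increase part of the QTcF flag against it as well. Keep the Day 1 baseline for Period 1, for temperature, respiratory rate and oxygen saturation, and as a parallel display in Period 2.

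The protocol wording already allows a specified exception, and no new measurements are needed. The cost is a short SAP edit, matching table shells and one extra change column. Two limits should be stated with the tables: drift from time or confinement after Day 6 remains, and the change for LOXO-305 plus cocktail still includes the preceding nine days (Days 6 to 14) of LOXO-305 alone.
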